4. SUBJECT DISPOSITION

4.1. Subject Enrollment and Disposition

A summary of subject enrollment will be provided for each investigator. The summary will present the number and percentage of subjects in the Safety Analysis Set. The denominator for the percentage calculation will be the total number of subjects analyzed.

A summary of subject disposition will be provided by region and genotype. This summary will present the number of subjects screened, the number of subjects enrolled, the number of subjects enrolled but never treated, and the number and percentage of subjects in each of the categories listed below. For the “Treated” category, the denominator for the percentage calculation will be the total number of subjects enrolled for each column. For all other categories, the denominator for the percentage calculation will be the total number of subjects in the Safety Analysis Set for each column.

- Treated (Safety Analysis Set)
- In FAS
- Continuing study treatment if applicable
- Completed study treatment
- Did not complete study treatment with reasons for premature discontinuation of study treatment
- Completed study
- Did not complete the study with reasons for premature discontinuation of study

Among subjects who completed study treatment and who discontinued study treatment, the number and percentage of subjects will be summarized for:

- Who had no HCV posttreatment Week 4 assessment and thereafter (No HCV FU-4 and thereafter)
- Who had HCV posttreatment Week 4 assessment but no HCV posttreatment Week 12 assessment and thereafter (With HCV FU-4 but No FU-12 and thereafter)

If a subject did not have any HCV RNA assessment ≥ 21 days after the last dose of any study drug (ie, lower bound of FU-4 visit for HCV RNA data), the subject is categorized as having “No HCV FU-4 and thereafter”. If a subject had the HCV FU-4 assessment but did not have any HCV RNA assessment ≥ 70 days after the last dose of any study drug (ie, lower bound of FU-12 visit for HCV RNA data), the subject is categorized as having “With HCV FU-4 but No FU-12 and thereafter”.

In addition, the total number of subjects who were enrolled, and the number of subjects in each of the disposition categories listed above will be depicted by a flowchart.

The following by-subject listings will be provided by region and subject ID number in ascending order to support the above summary tables:

- Disposition for subjects who complete study treatment and study
- Disposition for subjects who did not complete study treatment and/or study with reasons for premature discontinuation of study treatment and/or study
- Lot number and kit ID (if applicable)

4.2. Extent of Exposure

Extent of exposure to study drug will be examined by assessing the total duration of study drug exposure and the level of adherence to the study drug regimen specified in the protocol.

4.2.1. Duration of Exposure to Study Drug

Total duration of exposure to study drug will be defined as last dose date minus first dose date plus 1, regardless of any temporary interruptions in study drug administration, and will be expressed in weeks using up to 1 decimal place (eg, 4.8 weeks).

The total duration of exposure to study drug will be summarized using descriptive statistics (n, mean, SD, median, Q1, Q3, minimum, and maximum) and using the number (ie, cumulative counts) and percentage of subjects exposed through the following time periods: baseline (Day 1), Week1 (Day 7), Week 2 (Day 14), Week 4 (Day 28), Week 6 (Day 42), Week 8 (Day 56), Week 10 (Day 70), and Week 12 (Day 84). A 3-day window is applied to the last planned on-treatment visit to match with the protocol-specified visit window, ie, number of subjects exposed through week 12 is calculated as the number of subjects who were exposed to study drug for at least 81 days. Summaries will be provided by region for the Safety Analysis Set.

4.2.2. Adherence to Study Drug

The presumed total number of tablets administered to a subject will be determined by the data collected on the drug accountability CRF using the following formula:

$$\text{Total Number of Doses Administered} = \left(\sum \text{No. of Tablets Dispensed} \right) - \left(\sum \text{No. of Tablets Returned} \right)$$

The level of adherence to the study drug regimen will be assessed based on the total amount of study drug administered relative to the total amount of study drug prescribed at baseline.

The level of adherence will be expressed in percentage using the following formula:

$$\text{Level of Adherence (\%)} = \left(\frac{\text{Total Amount of Study Drug Administered}}{\text{Total Amount of Study Drug Prescribed at baseline}} \right) \times 100$$

Note: If calculated adherence is greater than 100%, the result will be set to 100%.

In this study, the total amount of SOF/VEL (400 mg/100 mg) prescribed for 12 weeks would require 84 tablets.

Subjects who prematurely discontinue study drug for lack of efficacy (ie, virologic failure) will have the total amount of study drug prescribed calculated up to the first date when virologic failure criteria were met. For virologic failure confirmed by 2 consecutive measurements the date of the first measurement will be used. If there are study drug bottles dispensed on or after the subject first met virologic failure criteria, these bottles will not be included in the calculation of adherence. If a bottle is dispensed and the bottle is returned empty, then the number of tablets returned will be entered as zero. If a bottle is dispensed but not returned (missing), the number of tablets taken from that bottle will be counted as zero.

Descriptive statistics for the level of adherence (n, mean, SD, median, Q1, Q3, minimum, and maximum) with the number and percentage of subjects belonging to adherence categories (eg, < 80%, ≥ 80 to < 90%, ≥ 90%) will be provided by region and genotype for the Safety Analysis Set.

No inferential statistics will be provided for duration of exposure and adherence to study drug.

A separate by-subject listing of study drug administration and drug accountability will be provided by region, subject ID number (in ascending order) and visit (in chronological order).

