3.7. Visit Windows

3.7.1. Definition of Study Day

Study day is the day relative to the date of the first dose of study drug. Study Day 1 will be defined as the day of first dose of study drug administration.

Study day will be calculated from the date of first dose of study drug administration and derived as follows:

- For postdose study days: Assessment Date – First Dose Date + 1
- For days prior to the first dose: Assessment Date – First Dose Date

The last dose date will be the end date on study drug administration eCRF for the record where the “subject permanently discontinued” flag is ‘Yes’.

If there are subjects for whom the date of last study drug is unknown due to the reason that the subject was lost to follow-up and not able to be contacted, the date of last dose will be estimated using the maximum of nonmissing study drug start or stop dates, visit dates and laboratory collection dates (posttreatment visits and unscheduled visits are not included).

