6.2. Secondary Efficacy Endpoints

6.2.1. Definition of Secondary Efficacy Endpoints

Secondary efficacy endpoints include the following:

- The percentage of subjects with HCV RNA < LLOQ 4 and 24 weeks after discontinuation of treatment (SVR 4 and SVR 24)
- The percentage of subjects with HCV RNA < LLOQ while on treatment by study visit
- HCV RNA (\log_{10} IU/mL) and change from baseline in HCV RNA (\log_{10} IU/mL) through end of treatment (EOT)
- The percentage of subjects with virologic failure as the following:

On-treatment virologic failure

- HCV RNA \geq LLOQ after having previously had HCV RNA < LLOQ, while on treatment, confirmed with 2 consecutive values (note, second confirmation value can be posttreatment), or last available on-treatment measurement with no subsequent follow-up values (ie, breakthrough)
- 1 \log_{10} IU/mL increase in HCV RNA from nadir while on treatment, confirmed with 2 consecutive values (note, second confirmation value can be posttreatment), or last available on-treatment measurement with no subsequent follow-up values (ie, rebound)
- HCV RNA persistently \geq LLOQ through 8 weeks of treatment (ie, nonresponse)

Relapse

- HCV RNA \geq LLOQ during the posttreatment period having achieved HCV RNA < LLOQ at end of treatment, confirmed with 2 consecutive values or last available posttreatment measurement
- Characterization of HCV drug resistance substitutions at baseline, during, and after therapy with SOF/VEL

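### For subjects who stop for virologic failure, adherence divides tablets taken partly after the first failing sample by tablets prescribed only up to it

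*SAP*

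**What the plan says.** Section 4.2.2 defines the numerator as tablets dispensed minus tablets returned, summed over bottles from the drug accountability CRF. The denominator is the amount prescribed at baseline; the full course "prescribed for 12 weeks would require 84 tablets". Results above 100% are set to 100%.

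Subjects who stop early for virologic failure get a special denominator: they "will have the total amount of study drug prescribed calculated up to the first date when virologic failure criteria were met". The date is fixed further: "For virologic failure confirmed by 2 consecutive measurements the date of the first measurement will be used". The matching rule for the numerator works by bottle: "If there are study drug bottles dispensed on or after the subject first met virologic failure criteria, these bottles will not be included". No rule removes tablets taken after the failure date from a bottle dispensed before it.

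Section 6.2.1 requires breakthrough and rebound to be "confirmed with 2 consecutive values (note, second confirmation value can be posttreatment"), or to be the last available on-treatment value with no follow-up. Appendix 1 schedules dispensing at Day 1, Week 4 and Week 8, and on-treatment HCV RNA at Weeks 1, 2, 4, 6, 8, 10 and 12.

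Adherence is summarised with categories at 80% and 90% by region and genotype. Section 3.3 also uses the 80% cut as an SVR12 subset, which Section 6.1.4 displays with exact confidence intervals.

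**The concern.** The special rules evidently aim to leave drug taken after failure out of the adherence measure. The denominator does this to the day. The numerator does it only to the bottle, so the two terms can cover different periods. Where they differ, the later tablets can make up for doses missed before failure, and the ratio is then adherence over no defined period.

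The error can only raise adherence, and it can arise only in subjects stopped for virologic failure, who would normally be SVR12 failures. Any move from <80% to ≥80% is therefore tied to the outcome: it takes a likely failure out of the low-adherence subset and puts it into the other one.

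**Working it through.** **Inputs.** One tablet daily for 12 weeks (Section 1.2): 12 × 7 × 1 = 84, which reproduces the SAP's full-course figure. Dispensing and sampling visits are from Appendix 1. The number of tablets taken after the first failing sample is not given in the SAP; 7 is used as an illustration, with 1 and 14 as a range.

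**Formula.** Let D be tablets prescribed to the first failing sample, m the tablets missed before it, and g the tablets taken after it from a bottle dispensed before it.

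- Adherence to the failure date: (D − m)/D.
- Reported value under Section 4.2.2: min{1, (D − m + g)/D}.
- Inflation: min(m, g)/D.

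If m = 0 the cap returns the correct 100%. If m > 0 and g > 0 the cap limits the excess but does not remove it.

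**When g > 0.** If the failing sample falls at Week 4 or Week 8, the bottle dispensed that day is excluded and the mismatch largely disappears. Nonresponse, HCV RNA persistently at or above "LLOQ through 8 weeks of treatment (ie, nonresponse"), is met at Week 8 and so largely escapes. What remains is breakthrough or rebound first met at Week 2, 6 or 10. Week 1 is not a realistic case. It is the first scheduled sample after Day 1, so breakthrough cannot first appear there on scheduled visits, and rebound would need the Day 1 value as the nadir.

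**Example, D = 42, m = 10, g = 7.** Adherence to failure: (42 − 10)/42 = 32/42 = 76.2%. Reported: (42 − 10 + 7)/42 = 39/42 = 92.9%. Inflation: 7/42 = 16.7 points. The subject moves from the <80% category to the ≥90% category.

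**Who crosses 80% when g = 7.** The subject must be below 80% without the 7 tablets and at or above it with them.

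| First failing sample | D | Tablets needed for ≥80% | Missed tablets (m) that cross | Largest inflation |
|---|---|---|---|---|
| Week 2, Day 14 | 14 | 12 | 3 to 9 | 7/14 = 50 points |
| Week 6, Day 42 | 42 | 34 | 9 to 15 | 7/42 = 16.7 points |
| Week 10, Day 70 | 70 | 56 | 15 to 21 | 7/70 = 10 points |

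**Sensitivity to g at Day 42.**

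- g = 1: inflation is at most 1/42 = 2.4 points, and only m = 9 crosses (33/42 = 78.6% to 34/42 = 81.0%).
- g = 14 (dosing to Day 56): m = 11 gives 31/42 = 73.8% to failure, reported as 45/42 = 107.1% and capped at 100%.

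**A common later end date.** Suppose both terms end 7 days after the first failing sample, with g = 7. The value becomes (D − m + 7)/(D + 7).

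- Day 42, m = 10: 39/49 = 79.6%, no crossing.
- Day 42, m = 9: 33/42 = 78.6% becomes 40/49 = 81.6%, still a crossing.
- Day 14, m = 3 or 4: 78.6% or 71.4% becomes 18/21 = 85.7% or 17/21 = 81.0%.
- Day 70, m = 15: 55/70 = 78.6% becomes 62/77 = 80.5%.

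The crossing values of m shrink from seven in each row of the table to two (Day 14), one (Day 42) and one (Day 70). The later date restores a defined period but does not recover adherence up to failure.

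**The case against.** The strongest reply is that this hardly matters. Section 4.2.2 plans no inferential statistics for adherence, the SVR12 subsets are exploratory, and the primary test compares Region 1 SVR12 with 85% without using adherence. The rule touches only subjects who stop early for virologic failure, between dispensing visits, after imperfect adherence; a shift across 80% needs more than 20% of doses missed by then. The 50-point entry for Day 14 needs 7 of the first 14 tablets missed and 7 taken afterwards, which is extreme and should not be read as typical. A second value may also come after treatment, so g may be small or zero. All of this stands. It limits the size of the problem but does not make the two periods agree.

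A reader might infer that the neighbouring rule for lost bottles is also a fault: "If a bottle is dispensed but not returned (missing), the number of tablets taken from that bottle will be counted as zero". The SAP does not support that. The rule is an explicit, conservative convention, it contradicts nothing, and the planned by-subject accountability listing lets unreturned bottles be identified. A further sensitivity display would be a preference.

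A reader might also infer that every subject who stops for virologic failure has inflated adherence. That is not so: full adherence before failure, or failure first met at a dispensing visit, gives the right or nearly the right value.

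**Conclusion.** The mismatch follows directly from the wording of Section 4.2.2 and is minor. For an affected subject the inflation is min(m, g)/D: 16.7 points in the Day 42 illustration, and at most 2.4 points there if only one later tablet was taken. It can place a likely SVR12 failure in the wrong adherence subset. The number of subjects affected is unknown and probably small.

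The sizes rest on an assumed number of later tablets and on one tablet a day. That the mismatch exists, and that it can only raise adherence, depends on neither the assumed 7 tablets nor bottle size.

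**What to change.** End the numerator and the denominator at the same date for subjects who stop for virologic failure. The best choice is the visit of the first failing sample, using the tablet count reconciled there. This keeps the SAP's intention of measuring adherence up to failure. Appendix 1 already plans a compliance review at every on-treatment visit and requires subjects to bring all medication back for reconciliation at every visit after Day 1. Whether the CRF stores each count is not stated and should be checked. The visit-day dose should be treated alike in both terms.

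If the count is not stored, end both terms at the return of the bottle in use at the first failing sample, or at the last dose date if that is earlier. The latter is available: "The last dose date will be the end date on study drug administration eCRF" (Section 3.7.1). The SAP should then say that adherence for these subjects covers a period beyond failure and that some borderline subjects can still cross 80%.

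The cost is one or two sentences in Section 4.2.2 and a small derivation change before database finalization. No new display is needed.

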4.3. Protocol Deviations

A summary of important protocol deviations will be provided by the Clinical Operations group for subjects in the Safety Analysis Set.

A by region, by-subject listing will be provided for those subjects who violate at least 1 inclusion or exclusion criterion. The listing will present the entry criterion (or criteria if more than 1 violation) that subjects did not meet and related comments, if collected.

5. BASELINE CHARACTERISTICS

5.1. Demographics

Subject demographic variables (ie, age, sex, race, and ethnicity) will be summarized by region and genotype using descriptive statistics (n, mean, SD, median, Q1, Q3, minimum, and maximum) for age, and using the numbers and percentages of subjects for age categories (< 65 years, ≥ 65 years), sex, race, and ethnicity. Age is calculated in years at the date of initial study drug administration. If a subject did not receive study drug after enrollment, the subject's age will be calculated from the date that the subject signed the informed consent form. The summary of demographic data will be provided for the Safety Analysis Set.

A by-subject demographic listing, which includes the date the informed consent was signed, will be provided by region and subject ID number in ascending order.

5.2. Baseline Characteristics

Baseline characteristics include:

- body mass index (BMI; in kg/m^2) as a continuous variable and as categories ($< 25 \text{ kg}/\text{m}^2$, $\geq 25 \text{ kg}/\text{m}^2$)
- HCV genotype and subtype
- IL28B (CC, CC, non-CC; with non-CC further broken down to CT, TT)
- baseline HCV RNA (\log_{10} IU/mL) as a continuous variable and as categories ($< 800,000 \text{ IU}/\text{mL}$, $\geq 800,000 \text{ IU}/\text{mL}$; $< 5 \log_{10} \text{ IU}/\text{mL}$, $\geq 5 \log_{10} \text{ IU}/\text{mL}$)
- baseline ALT (U/L) as a continuous variable and as categories ($\leq 1.5 \times \text{ULN}$, $> 1.5 \times \text{ULN}$)
- cirrhosis (presence, absence, missing)
- cirrhosis determination method (Liver Biopsy, Fibrotest/APRI, Transient Elastography, Fibrotest/APRI and Transient Elastography, and Not determined per protocol)
- prior HCV treatment experience (treatment naïve, treatment experienced)
- prior HCV treatment (DAA+PEG+RBV, INTERFERON+RBV, PEG+RBV, Other) for treatment-experienced subjects
- most recent HCV treatment response (non-responder, relapse/breakthrough, early treatment discontinuation, met a virologic stopping rule, not otherwise listed, unknown) for treatment-experienced subjects
- estimated glomerular filtration rate (eGFR) using the Cockcroft-Gault equation

eGFR will be calculated by the Cockcroft-Gault method: $eGFR_{CG} \text{ (mL/min)} = [(140 - \text{age (yrs)}) \times \text{weight (kg)} \times (0.85 \text{ if female})] / (\text{serum creatinine (mg/dL)} \times 72)$, where weight is total body mass in kilograms.

These baseline characteristics will be summarized by region and genotype using descriptive statistics (n, mean, SD, median, Q1, Q3, minimum, and maximum) for continuous variables and using the numbers and percentages of subjects for categorical variables. The summary of baseline characteristics will be provided for the Safety Analysis Set.

A by-subject listing of baseline characteristics will be provided by region and subject ID number in ascending order.

A separate by-subject data listing for cirrhosis determination will be provided for all subjects at screening.

A separate by-subject data listing for prior HCV treatment and response will be provided for all treatment-experienced subjects. The listing will display the prior HCV regimen(s) and treatment(s) including the treatment duration, and the prior HCV treatment response.

5.3. Medical History

A by-subject listing of disease-specific medical history will be provided by region and subject ID number (in ascending order) and medical history of abnormalities (in chronological order).

6. EFFICACY ANALYSES

6.1. Primary Efficacy Endpoint

6.1.1. Definition of the Primary Efficacy Endpoint

The primary efficacy endpoint is SVR12 defined as HCV RNA < LLOQ 12 weeks after discontinuation of all study drugs in the FAS. The COBAS[®] TaqMan[®] HCV Quantitative Test, v2.0 for use with Amplicrep will be used to measure HCV RNA.

6.1.2. Statistical Hypothesis for the Primary Efficacy Endpoint

In the primary efficacy analysis, the SVR12 rate in Region 1 will be compared to the pre-specified performance goal of 85% by using a two-sided exact one-sample binomial test at the 0.05 significance level. The null (H0) and alternative (H1) hypotheses used to assess superiority of SOF/VEL in Region 1 relative to the performance goal of 85% are:

- H0: SVR12 rate = 85%
- H1: SVR12 rate \neq 85%

It is difficult to characterize a single historical control rate for all genotypes included in this study given the different standards of care of each genotype (some of which include interferon), and the lack of historical data for genotype 4, 5, and 6 participants. Given these difficulties, rather than use a historical control rate as the basis for assessing the primary endpoint, a pre-specified performance goal is defined as a benchmark against which the efficacy of SOF/VEL will be tested. The benchmark sets a high bar of 85%. The basis for this benchmark includes the overall trend toward increasing SVR rates in recent years, the higher SVR rates observed with Peg-IFN + RBV treatment in Chinese and other Asian subjects {Yu 2009} compared with other races, and the general appeal of using a fixed clinically relevant threshold as a measure of treatment benefit {Weins 2013} of SOF/VEL.

6.1.3. Primary Analysis of the Primary Efficacy Endpoint

The 2-sided 1-sample exact binomial test will be used to test the statistical hypotheses described above. The 2-sided 95% exact confidence interval (CI) based on the Clopper-Pearson method {Clopper 1934} will be provided for the SVR12 rate for Region 1.

The point-estimate with the 2-sided 95% exact confidence interval (CI) using the binomial distribution (Clopper-Pearson method) will also be constructed for the SVR12 rates for Region 2 and for the overall population.

6.1.4. Subgroup Analysis of the Primary Efficacy Endpoint

Point estimates and 95% exact confidence intervals (CIs) of the SVR12 rates by region and genotype will be displayed for each subgroup outlined in Section 3.3.

A Forest plot will graphically present estimates and 95% CIs on the SVR12 rates for each of the subgroups.

6.2. Secondary Efficacy Endpoints

6.2.1. Definition of Secondary Efficacy Endpoints

Secondary efficacy endpoints include the following:

- The percentage of subjects with HCV RNA < LLOQ 4 and 24 weeks after discontinuation of treatment (SVR 4 and SVR 24)
- The percentage of subjects with HCV RNA < LLOQ while on treatment by study visit
- HCV RNA (\log_{10} IU/mL) and change from baseline in HCV RNA (\log_{10} IU/mL) through end of treatment (EOT)
- The percentage of subjects with virologic failure as the following:

On-treatment virologic failure

- HCV RNA \geq LLOQ after having previously had HCV RNA < LLOQ, while on treatment, confirmed with 2 consecutive values (note, second confirmation value can be posttreatment), or last available on-treatment measurement with no subsequent follow-up values (ie, breakthrough)
- 1 \log_{10} IU/mL increase in HCV RNA from nadir while on treatment, confirmed with 2 consecutive values (note, second confirmation value can be posttreatment), or last available on-treatment measurement with no subsequent follow-up values (ie, rebound)
- HCV RNA persistently \geq LLOQ through 8 weeks of treatment (ie, nonresponse)

Relapse

- HCV RNA \geq LLOQ during the posttreatment period having achieved HCV RNA < LLOQ at end of treatment, confirmed with 2 consecutive values or last available posttreatment measurement
- Characterization of HCV drug resistance substitutions at baseline, during, and after therapy with SOF/VEL

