6.2.2. Analysis Methods for Secondary Efficacy Endpoints

For analyses of HCV RNA < LLOQ by visit while on treatment and during the posttreatment (SVR) follow-up period, subjects will be assigned a value at each visit based on the analysis visit windows specified in Section 3.7.2. Missing values will be imputed based on the categorical imputation rules described in Section 3.4.1. The two-sided 95% exact confidence interval based on Clopper-Pearson method will be provided for the percentage of subjects with HCV RNA < LLOQ at each visit by region and genotype. The overall category for “HCV RNA < LLOQ” will be split into the following 2 subcategories: “< LLOQ TND” for subjects with target not detected and “< LLOQ detected” for subjects with < LLOQ detected in tabular displays.

Graphs for the percentage of subjects with HCV RNA < LLOQ over time during treatment will be displayed.

Summary statistics will be presented for absolute values and change from baseline in HCV RNA (\log_{10} IU/mL) by visit through EOT. Imputation rules described in Section 3.4.1 will be used to assign HCV RNA values for missing values at a visit that are bracketed by “< LLOQ TND” and/or “< LLOQ detected”. Otherwise, a missing = excluded analysis will be performed. Plots of the mean \pm SD and median (Q1, Q3) of absolute values and changes from baseline in HCV RNA through EOT will be presented.

For the SVR12 endpoint analysis, a summary table of the number and percentage of subjects with SVR12, virologic failure (VF), and Other by region and genotype will be created. All subjects who achieve SVR12 will be categorized as SVR12. Virologic failure will be descriptively summarized as “on-treatment virologic failure” and relapse (which will be broken down by study drug completed yes/no). Subjects who do not achieve SVR12 and do not meet criteria for VF will be categorized as “Other”. The denominator for relapse will be the number of subjects who had HCV RNA < LLOQ on their last observed on-treatment HCV RNA measurement; otherwise, the denominator will be the number of subjects in the FAS.

[figure not shown]
A concordance table between SVR12 and SVR24 will be provided by region and genotype. Subjects with both observed SVR12 and observed SVR24 data will be included for this analysis.

Drug resistant substitutions will be analyzed and presented as part of the Clinical Study Report.

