- g Subjects must be instructed to bring back all medication in the original container at every post-Day 1 study visit through the end of treatment. Study medication will be reconciled at every post-Day 1 visit by the investigator in order to monitor the subject's adherence with the medication regimen.
- h PPD
- i All subjects will complete Post treatment Week 4. Subjects with HCV RNA $<$ LLOQ at the post treatment Week 4 and/or Week 12 visits will complete the subsequent post treatment visits, unless viral relapse is determined.
- j Plasma samples will be collected for possible viral resistance and other Virology studies

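### The relapse rule rests on HCV RNA level alone, so infection with a new strain before SVR12 is established must be tabulated as SOF/VEL relapse

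*SAP*

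**What the plan says.** - **Definition (SAP 6.2.1).** Relapse is HCV RNA at or above LLOQ "during the posttreatment period having achieved HCV RNA < LLOQ at end of treatment, confirmed with 2 consecutive values" or, alternatively, standing as the last posttreatment value on record. Nothing is said about genotype, subtype or sequence.
- **Outcome table (SAP 6.2.2).** There are three categories. First, "All subjects who achieve SVR12 will be categorized as SVR12". Second, "Virologic failure will be descriptively summarized as" on-treatment failure and relapse. Third, "Subjects who do not achieve SVR12 and do not meet criteria for VF will be categorized as" Other. The relapse denominator is the subjects whose last on-treatment HCV RNA was below LLOQ.
- **Timing (SAP 3.7.2 and 3.7.3).** The FU-12 HCV RNA window runs from day 70 to day 146 after the last dose, and the latest record in the window is used.
- **Resistance (SAP 6.2.1 and 6.2.2).** The endpoint is "Characterization of HCV drug resistance substitutions at baseline, during, and after therapy with SOF/VEL". The analysis itself is left to the clinical study report.
- **Samples (SAP Appendix 1).** HCV genotyping is done at screening. Viral sequencing/phenotyping samples are scheduled from Day 1 through the posttreatment visits. Footnote j gives their purpose: "Plasma samples will be collected for possible viral resistance and other Virology studies".

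Reinfection is not mentioned in the readable text of the SAP.

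**The concern.** HCV RNA can return after treatment because the treated virus was not cleared or because the subject was cured and then infected with another strain. Only the first is a failure of SOF/VEL. The stated rule cannot tell them apart, and the outcome table forces both into relapse.

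The proportion with virologic failure is a secondary objective (SAP 1.1) and is reported by region and genotype. A new infection, even with a different genotype, would appear as a relapse in the column of the subject's baseline genotype. The study is open-label with no comparator arm, so there is no second group in which the same misclassification would show. If the question arises only after a relapse has been seen, any reclassification will look like a choice made in the drug's favour.

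**Working it through.** **1. The plan's own figure.** The SAP gives no relapse or reinfection figure. Its related figure is the power of the Region 1 SVR12 test (SAP 1.3): n = 260, 85% against 85% + 6 = 91%, exact two-sided test at 0.05, stated as more than 80%.
- Upper rejection region: 233 or more responders, since P(X ≥ 233 | 260, 0.85) = 0.0193, which is below 0.025.
- Power: P(X ≥ 233 | 260, 0.91) = 0.815, or 81.5%. The stated figure reproduces.
- A reinfected subject with HCV RNA at or above LLOQ at FU-12 is not SVR12 under either label, so the test and its power do not change.

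**2. Tracing subjects through the rules.** Each subject was below LLOQ at the last on-treatment measurement.

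| Course after treatment | SVR12? | Meets relapse wording in 6.2.1? | Cell in the 6.2.2 table |
|---|---|---|---|
| New strain; HCV RNA ≥ LLOQ at FU-12, confirmed or last value | No | Yes | Relapse |
| Below LLOQ early in the FU-12 window; new strain and ≥ LLOQ on a later record up to day 146, confirmed or last value | No (latest record used) | Yes | Relapse |
| New strain after SVR12 is established | Yes | Yes, taken alone | SVR12; visible only as SVR12/SVR24 discordance |
| Single value ≥ LLOQ, then below LLOQ | Depends on FU-12 record | No | Not relapse |

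In the first two rows Other is closed, because it admits only subjects who do not meet the failure criteria. The numerator rises by 1. The denominator, fixed at end of treatment, does not change. The bias therefore has one direction.

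**3. Size per case.** Planned numbers come from SAP 1.2:
- Overall: 1/360 = 0.28 points.
- Region 1: 1/260 = 0.38 points.
- A 60-subject Region 1 genotype cohort: 1/60 = 1.7 points.

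The true denominator may be a little smaller, which makes each step slightly larger.

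**4. How many cases (assumption only).** The SAP gives no reinfection rate. For illustration, assume 0.5 to 10 per 100 person-years, with all 360 at risk from the last dose. Expected cases = 360 × rate × weeks / 52.18.
- To Week 12: 360 × 0.005 × 12 / 52.18 = 0.4, up to 360 × 0.10 × 12 / 52.18 = 8.3 (0.1% to 2.3%).
- To day 146 (146/7 = 20.9 weeks), the outer limit of the FU-12 window: 0.7 to 14.4 (0.2% to 4.0%).

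**5. Effect on a reported rate (assumed counts).** With 10 relapses in 360, the rate is 2.8% (95% exact CI 1.3 to 5.1). If 2 of the 10 were reinfections, it would be 8/360 = 2.2% (1.0 to 4.3).

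**The case against.** The strongest reply is that relapse defined by HCV RNA level is internally consistent and errs against the drug. Virologic failure is only described, not tested. The protocol, not available for this review, may hold a virology rule, and footnote j leaves room for a strain comparison. Separating reinfection can only lower the relapse count, and only where a usable sequence pair exists.

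Much of this stands. No stated inference changes, and a rule elsewhere cannot be excluded. But the SAP does more than stay silent: it states a definition and a closed set of categories that together assign the wrong label. That reclassification favours the drug is a reason to fix the rule in advance.

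A reader might draw stronger conclusions that the SAP does not support:
- **Every posttreatment return counts as failure.** It does not. An isolated value followed by one below LLOQ is not relapse, and subjects with SVR12 stay SVR12 in the table. For the same reason the error in that table does not keep growing to Week 24.
- **Reinfection will be reported as emergent resistance.** This is possible but not shown. The SAP sets out no resistance method, and a comparison of baseline and posttreatment sequences could itself reveal an unrelated strain.
- **Reinfection makes up a large share of relapses.** Any such share rests on assumed relapse and reinfection rates.

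**Conclusion.** The point holds within a defined scope. Under SAP 6.2.1 and 6.2.2, infection with a different strain before SVR12 is established, once confirmed or recorded as the last value, must be counted as SOF/VEL relapse. The bias is upward only: about 0.28 points per case overall, 0.38 in Region 1 and 1.7 in a 60-subject genotype cohort. The number of cases cannot be derived from the SAP; the counts in steps 4 and 5 of the working are illustrations.

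Returns after SVR12 do not inflate the tabulated relapse rate, but the SVR12/SVR24 concordance table would show them with no rule for their cause. The effect is confined to a descriptive secondary endpoint. The SVR12 analysis, its test and its power are unchanged. The change is worth making because the samples are already scheduled and the rule is credible only if set before results are known.

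**What to change.** Before database finalization, add to SAP 6.2.1 and 6.2.2:

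1. For each subject who meets the relapse criteria, or whose SVR12 and SVR24 results disagree, the posttreatment virus is compared with the screening genotype and the Day 1 sequence, using the samples already scheduled.
2. Demonstrated different-strain cases go in a separate reinfection row. They remain not SVR at that time point but leave the relapse numerator.
3. These subjects are flagged in the resistance analysis so that the new strain's substitutions are not called treatment-emergent.
4. Subjects without a usable sequence pair remain relapse.
5. The relapse rate is also shown with reinfections counted as relapse.

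If the protocol or a virology plan already has such a rule, a cross-reference and the table row are enough.

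The cost is SAP wording, one table row and one additional rate. The downside is small: the relapse count will depend on a sequence comparison in a few subjects, and reclassification can only favour the drug. Items 4 and 5 and prespecification guard against that.
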